## **II. Methods to address Secondary Aim 3: To assess clinician and staff satisfaction with the eReferral and paper F2Q systems.**

In addition to our systematic testing of the impact of eReferral relative to F2Q in terms of rates of smokers to the WTQL as well as cessation rates of those enrolling in WTQL services, we will conduct brief pre- and post-electronic questionnaire surveys of all clinic staff regarding their experience with the two methods of referring patients who smoke to the WTQL. The pre-survey will be sent electronically to all staff members during the three-month Preparation Phase and the post-survey will be sent at six months post-initiation of the study in each clinic. Staff to be surveyed include the Medical Assistants, nurses, clinic manager, and provider staff (physicians, nurse practitioners, and physician assistants). The surveys will be designated by clinical role and will not be further identified. The survey will be designed to target constructs (both "facilitators of" and "obstacles to" adoption of EHR and workflow enhancements) that are implicated by prior research on adoption and maintenance of system changes:

- Task/job training and understanding
- Personal attitudes about smoking
- Appropriateness of activity for role
- Perceived importance to patient and to clinic
- Self-efficacy for task
- Feeling of team membership

Finally, open-ended items on the survey will help ensure that information is gathered on unanticipated or unusual issues that affect referring patients to the Wisconsin Tobacco Quit Line. These surveys are similar to those used extensively in our earlier research on smoking intervention in clinic settings. They were designed to meet high standards with regards to item writing and psychometrics (e.g., Devellis, 2012). The survey to be used for this pre- and post-survey is provided as Appendix A.

2/28/2017 Amendment. The staff survey developed for eReferral to the Quitline has been adapted slightly to assess familiarity with and beliefs about text support programs prior to and after eReferral launch and to assess use of and attitudes toward SmokefreeTXT at the end of the eReferral evaluation period in each clinic. The adapted version of the staff survey is shown in Appendix B. Items I-X and XIX-XX are identical to those used in the existing protocol for Quitline referral. Items XI-XVIII, XXI, and XXIIC

are specific to SmokefreeTXT. We are only asking about experience referring patients to SmokefreeTXT after study launch because we expect very few clinical staff to have knowledge of or experience with SmokefreeTXT prior to eReferral training and launch. Clinics in the existing protocol had experience with fax-to-quit programs for Quitline referrals, but have no such history with SmokefreeTXT or other text-message-support programs for smoking cessation.

9/19/2019. The items in the survey have not been changed, but items that previously only applied to clinicians now apply to rooming staff who will make the SmokefreeTXT referral offer to patients.

Dependent Variables for Intervention Phase: Acquisition & Appraisal: The tobacco quitline vendor (Optum) will derive summary data on an ongoing basis from both the F2Q and the EHR-based referrals with patient specific identifiers removed and provide such summary data to study staff. These summary data forms will allow us to compute the following monthly outcomes linked to clinic: (1) number of referrals to the quitline, (2) number of successful WTQL contacts with patients, and (3) number of quality WTQL contacts with the patient (where the patient enrolls in and receives tobacco quitline services). This quitline information will supplement information provided by the clinic's EHR system (both F2Q and eReferral clinics have identical Epic EHR systems) That is, the number of quitline referrals can be divided by the total number of tobacco users since participating clinics must have accurate estimates of tobacco users seen in each clinic/month to compute a clinic smoker referral rate. Thus, these outcomes will address how many patient tobacco users are *referred* to the quitline each month (via the fax or EHR-based referral mechanism), the number of these referred patients whom the quitline successfully contacts/month, and the number of these patients who enroll in a quitline counseling program/month (quality contacts). We can also determine the proportion of quality contacts by dividing the number of quality contacts by the total contacts. These measures will also be computed on a per month basis by clinic so as to capture such outcomes as contacts/month, quality contacts/month, and referrals/month.

2/28/2017 Amendment. For evaluation of eReferral to SmokefreeTXT, dependent variables will parallel those in the existing protocol for Quitline eReferral. The SmokefreeTXT vendor (ICF International) will send summary data regarding the number of eReferrals received and the number of patients engaged by clinic to study staff no less than monthly. These summary data will indicate how many eReferrals were received, how many were successfully enrolled in the program (i.e., who had a working number), how many of those enrolled dropped out by texting STOP to the program, and, finally, how many texted responses indicating no smoking vs. any smoking in the last 7 days 6 weeks post-target-quit date. Aggregate EHR data will be pulled from the health system at the end of the study to ensure that the number of eReferrals received by ICF International is consistent with the number of eReferrals sent, as recorded in the EHR. These EHR reports will also indicate the total number of patients seen, the total number of visits completed, the total number of patients who smoke seen, and the total number of visits completed by patients who smoke during the active eReferral evaluation period in each clinic, as well. This will be used to determine the rates of referral, engagement, and retention in SmokefreeTXT.

UW-CTRI will evaluate the principal dependent measures on the basis of rate of tobacco users referred to the WTQL/month, showing changes from the baseline to the post-intervention periods on the basis of percentage of tobacco user referral or contact status/tobacco user flow at each clinic. The public health importance of this research will be seen if the EHR-based program results in rates of referrals and contacts (and quality referrals and contacts) that are higher, more uniform, and more sustained across time, than are generated by the F2Q method. It is possible that changes in contact rates from the baseline period to the post-intervention period may reflect correlated secular changes or simply the

passage of time. Therefore, we will keep track of potentially relevant secular events. In addition, because the F2Q control and the EHR referral clinics will enter the study on the same time line, the occurrence of secular changes should not differentially affect the two conditions.

For both the F2Q and eReferral systems, data acquisition to establish WTQL referral rates will be derived from monthly reports to UW-CTRI from the WTQL. Referral rates are based on a denominator reflecting the number of adult tobacco users seen in the study clinics per month during the study time periods; this will be obtained for both referral systems by querying an existing EHR field for all clinic EHR systems that reflect response to an existing vital signs question regarding tobacco use. Such data will be available for both the baseline and post-intervention periods. Thus, the method and presumably the reliability of the data acquisition process will be equivalent across the two study arms.

In order to obtain data for the secondary analysis of smoking abstinence among referred participants, the study will use standard WTQL follow-up evaluation procedures. The standard procedure of the WTQL is to obtain consent to conduct follow up as part of each registration process. The tobacco quitline routinely conducts follow up evaluations of quitline users for QI and self-evaluation purposes four months post registration. Per the study team's request, aggregate follow-up data of four-month 7-day point-prevalence self-reported smoking status, quitting intentions, and other tobacco and tobacco cessation medication use on up to fifty patients completing the follow-up per clinic will be provided to study staff. Cessation rates will be projected separately by the number of tobacco patients visiting each clinic, those referred for quitline services, and those who enroll in WTQL following referral for both the paper faxed-based and EHR-based referral systems. Only patients who register for and agree to be followed up by the quitline will be contacted by the quitline for follow up.

2/28/2017 Amendment. As in the existing protocol, aggregated EHR data will be gathered to determine the number of patients seen per clinic per month in the study, including the number of tobacco using patients seen, and this will be used as the denominator in calculations of the rate of eReferral to SmokefreeTXT. In contrast to the existing protocol evaluating eReferral to the Quitline, there will be no comparison condition in this pilot study. Analyses will focus on the rate of uptake (eReferrals), drop out during the 6-8 week program, and smoking status at six-weeks post-quit. Assessment of smoking status six weeks post-quit is standard practice in the SmokefreeTXT program, along with assessment of smoking status, reset quit dates, craving, mood, and slips throughout the program. As such, there are not additional assessments proposed for the research study; all are standard parts of the SmokefreeTXT program. Data shared for eReferral evaluation purposes will be deidentified and/or aggregated.

**Hypotheses & Analytic Plan for Intervention Phase:** Specific quantitative hypotheses to be tested are-

- The fax referral training and the EHR-based referral training and intervention will both increase tobacco user quitline referrals and contacts, and quality referrals and contacts, during the post-intervention period relative to the baseline period. This pattern will be seen when examining monthly and aggregate /clinic data.
- The EHR-based referral intervention will be more effective than the fax referral intervention in increasing tobacco user quitline referrals and contacts, and quality referrals and contacts, in the post-intervention period relative to the baseline period. This superiority will be seen in /clinic data. Thus, while both interventions will increase contacts relative to baseline, the EHR-based referral will be especially effective in this regard.

Note that this second hypothesis implies the presence of an interaction between intervention condition and the two experimental periods (baseline and post-intervention).

- The EHR-based referral intervention process will increase smoking cessation outcomes more than does the fax referral mechanisms during the post-intervention phase. This will be seen when examining quit rate/clinic data.

The analysis of the primary outcome is designed to show differences in the rate at which patients are referred to the Wisconsin Tobacco Quitline by the 12 control (F2Q) versus the 12 experimental (EHR referral) clinics during the post-intervention period. We will use a mixed effects logistic regression model via Generalized Estimating Equations (via SAS PROC GENMOD; for a population based model) with coding for the baseline and post-intervention phases, and with coding for each post-intervention monthly time point with the models centered at the 6-month post-intervention mark. Based on data from the healthcare systems, we anticipate that on average, each clinic will see about 120 smokers/month, and based upon the urn randomization procedure we expect similar smoker flow rates across the two experimental conditions. The binary dependent variable will be measured at the smoker level, i.e., whether or not a smoker seen at a clinic is referred to the quitline, and aggregated to the clinic level to constitute clinic referral rate. Thus, while clinic is the unit of analysis, our sample is the smoker, each one being one Level 1 unit. Experimental condition will be coded with a single dummy variable. The baseline WTQL referral rate data for each clinic will serve as a covariate (only one covariate will be used to preserve degrees of freedom). We will specify a logit link function and assume a first-order autoregressive structure (to address dependence across measurement occasions). We will test the main effects of experimental conditions. Further, we have an a priori plan to test for post-intervention change over time within each experimental condition and will test for interaction between experimental condition and measurement occasion. Similar analyses will be used for the quality referral outcome.

In a subsequent model we will analyze cessation rates of tobacco patients identified as smokers during a clinic visit. Abstinence will be measured at the smoker level and aggregated to the clinic level by the WTQL to determine a clinic quit rate. We anticipate that there will be no overlap in rates of abstainers/clinic (abstainers from a clinic/smokers presenting to clinics within the relevant time period) for the two experimental conditions, permitting use of a non-parametric analysis of outcome (e.g., Mann-Whitney U).

2/28/2017 Amendment. Given that the objective of the SmokefreeTXT eReferral pilot study is to assess the feasibility, uptake, retention, and quit rates of this program, there are no specific quantitative hypotheses to test or comparisons to be conducted. Instead, analyses will be descriptive and will focus on uptake, retention, and quit rates by clinic. We will also assess staff knowledge of smoking cessation treatments and SmokefreeTXT-specific knowledge, practices, and attitudes prior to and after six months of SmokefreeTXT eReferral, with the expectation that knowledge, positive attitudes, and treatment practices among clinic personnel will improve from pre- to post-launch. In addition, we will document implementation challenges and solutions to inform future evaluation or dissemination efforts.

**Power Analyses for Intervention Phase:** Power was calculated for a two-group cluster-randomized design with clinic as the unit of randomization (n=6 clinics per group for each health system) with a conservative estimate of approximately 90 smokers seen in each clinic per month. The dependent variable for the power analysis is the proportion of smokers referred/month. We based our estimates of

the mean number of monthly referrals in each group on pilot data from an eReferral demonstration project (Adsit et al., 2014) which found a rate of 14% for an eReferral system versus 0.3% for a paper fax referral system^4. To achieve a more conservative power analysis, we calculated power to detect a smaller difference between the groups. More specifically, we estimated power to detect a group difference on proportion referred per month with values of 2% for the Fax to Quit group versus 7% for the eReferral group. As shown in Table 3, the groups are not expected to differ at baseline (mean of 1% referrals per month for each group). As such, the power analysis was based on a test of the difference between groups for the post-intervention proportion of referrals per month (2 vs 7%). The following power analysis therefore should be conservative since it does not take advantage of baseline referral rate to index change and its projected effect size is considerably less than might be expected based on prior research. For purposes of power analysis, we assumed that the standard deviation for the mean proportion of referrals per month will be 2.5%; we also set alpha at .05 for a two-tailed test. The power analysis was computed via an online program, GLIMMMPSE, that permits power estimation for cluster-randomized designs. Results of the power analysis showed that there is >90% power to detect a mean difference of 1 versus 7% of smokers referred per month. The demonstration of this effect within two health systems will allow even greater confidence in these primary outcomes.

**Table 3. Predicted Mean Rates of Quitline Contacts/Clinic/Month as Proportions of Smokers Seen, Two Arms Across Baseline and Intervention Phases**

Intervention Arm	Baseline	Intervention
Fax Referral (Fax to Quit)	1%	2%
EHR-based Referral (eReferral)	1%	7%

2/28/2017 Amendment. Formal power analyses were not conducted for the pilot test of the feasibility of eReferral to SmokefreeTXT that will be conducted in 1-3 clinics.

**Staff Survey Analysis.** Most items on the survey are Likert scale items so their scoring and synthesis will be straightforward. We will compute standard psychometric indices such as item means, variance/standard deviation, and range. We will not subject items to factor analyses or determine coefficient alpha since the items were not designed to index latent dimensions. However, reliability/generalizability analyses will be conducted to determine if level of endorsement varies with type of staff member (this will be done across clinics, within each experimental condition). In formal analyses, we will use GEE (see above) to perform item-specific analyses since respondents will be nested within clinics. Thus, clinic will be treated as a Level 2 variable while staff member will be treated as a Level 1 unit. Because surveys will not carry personal identifiers we will conduct separate analyses on baseline and post-intervention data. The main analyses will test for differences in post-intervention endorsement levels as a function of experimental condition. In a subanalysis we will separately analyze data from the MA's, the only staff group large enough to permit dedicated analysis. These analyses will be repeated for the baseline data. Open ended items will be nonquantitatively synthesized and common or significant themes will be extracted and used to guide interpretation of the survey data.

2/28/2017 Amendment. As in the existing quit line eReferral protocol, staff survey analyses will focus on item means, variance/standard deviation, and range prior to and six months after the SmokefreeTXT eReferral launch. Given that only 1-3 clinics will be involved in the SmokefreeTXT eReferral pilot, however, we will not treat data as nested in clinic and will not examine results by staff role within clinics, and the numbers of particular staff types will be too low to support such an analysis. Survey data will be assessed and coded in the same way in the existing protocol and the SmokefreeTXT pilot.

Figure 1. Manual Fax to Quit: Clinic, Patient, and Data Workflow

[figure not shown]

Figure 2. Fax to Quit Consent Form Used in Clinics

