A UW-CTRI Outreach Specialist will provide additional support to all 24 participating clinics to encourage referrals to the WTQL modeled on typical clinical performance feedback activities. Specifically, this periodic support will include: 1) a one-week post-intervention launch, telephone or email check-in by UW-CTRI staff with both the Clinic Manager and the Physician Leader of each clinic, focusing on early challenges and problem solving as well as emphasizing the importance of systematically identifying tobacco users and referring (either via F2Q or eReferral) all appropriate patients to the tobacco quitline (“quality contacts”), 2) Monthly performance feedback will be shared with all staff and will include rates of F2Q or eReferrals from each clinic as well as data on the quality of the referral - the proportion of referrals that result in tobacco users who engage in quitline counseling (“quality contacts”). Specific performance feedback on the number of referrals and the number who accepted service will be provided for the clinic as a whole. Finally, 3) clinic staff will be provided with e-mail and telephone access to UW-CTRI staff who will be available to respond to questions or concerns about the F2Q or eReferral program.

At about one month after the launch of the intervention, all clinics will receive a refresher training (about 20 min) based on their randomized condition (F2Q vs. eReferral). Attempts will be made to piggy-back all trainings onto existing staff meetings. In total, rates of referral to the WTQL from all 24 clinics will be monitored for 6 months after the initial training. In this way we will compare the number and quality of quitline referrals between the six clinics randomized to the F2Q system and the six randomized to the e-Referral mechanism for receipt of WTQL treatment services.

2/28/2017 Amendment: This pilot SmokefreeTXT eReferral evaluation project will take place in 1-3 clinics (depending on clinic size, patient flow, and smoking prevalence in the clinics) over 12-17 months. This will include 2-4 months to finalize and troubleshoot the eReferral technological specifications with ICF International, Epic Systems, and Gundersen Health System Information Technology staff and then 6-9 months of testing of SmokefreeTXT eReferral engagement, retention, and effectiveness. Effectiveness testing will end 8 weeks after the end of eReferral implementation in each of the clinics, so eReferrals will end 8-11 months post-launch.

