**Clinic Randomization:** Once each of the 2 sets of 12 clinics are identified and agree to participate, they will be stratified within each health system and randomized into the two study conditions using Urn randomization (NOTE: one clinic from each system will serve as an eReferral pilot clinic to test the eReferral technology). In this methodology, the project MATCH randomization beta program will be used to equate the two clinic groups with respect to three factors: approximate number of primary care providers, approximate smoking prevalence amongst the adult patients seen during the one-year baseline period, and approximate rate of F2Q referral for all tobacco users seen during the baseline period. Each of the 24 identified clinics will be randomized into one of the following two intervention conditions: a) six per health system to continue with the existing F2Q WTQL referral system (Fax to Quit) and b) six per health system to transition to an EHR-based WTQL referral system (eReferral)

2/28/2017 Amendment. The 1-3 clinics for pilot testing of SmokefreeTXT eReferral will not be randomized; all will receive access to the EHR eReferral tools for 6-9 months during the study.

**Implementation Phase:** The following activities (with associated key outcomes) will take place over the twelve months of the Implementation Phase in each of the two study conditions (Table 2):

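### The primary GEE on 24 clinics names no variance estimator, reference distribution or small-sample correction and leaves out the randomisation stratum; both gaps should be closed together

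*Combined protocol and SAP*

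**What the plan says.** The inferential plan for both primary aims is one paragraph under Hypotheses & Analytic Plan for Intervention Phase in the combined protocol and SAP.

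- Model: "We will use a mixed effects logistic regression model via Generalized Estimating Equations (via SAS PROC GENMOD; for a population based model"; a logit link; one dummy variable for condition.
- Correlation: the analysis will "assume a first-order autoregressive structure (to address dependence across measurement occasions".
- Time: "with coding for each post-intervention monthly time point with the models centered at the 6-month post-intervention mark".
- Covariates: the baseline referral rate alone, because "only one covariate will be used to preserve degrees of freedom".
- Tests: the main effect of condition; the plan also "will test for interaction between experimental condition and measurement occasion".
- Primary Aim 2: "Similar analyses will be used for the quality referral outcome".

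The paragraph does not say whether standard errors are empirical or model-based, whether the test is Wald or score, which reference distribution applies, or whether there is a small-sample correction. A two-tailed alpha of .05 appears only under Power Analyses. The Staff Survey Analysis refers back to the same GEE and adds nothing on inference.

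On allocation, Clinic Randomization says of the clinics that "they will be stratified within each health system and randomized into the two study conditions using Urn randomization", with six clinics per condition in each system. The model has no health-system term.

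**The concern.** Two points need to be kept apart.

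First, the sandwich variance relies on a large number of clusters. With 24 clinics and a few clinic-level parameters it is biased downwards and is itself variable. Reading the Wald ratio against 1.96 then rejects too often and gives intervals that are too short. The plan does not commit to this test, but it does not exclude it either.

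Second, allocation was balanced within health system, but the analysis ignores system. If systems differ in referral, that difference stays in the residual variance although the design has removed it from the arm contrast.

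At stake are the size of the primary tests, the coverage of their intervals, and a choice of method that could otherwise be made after the data are seen.

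**Working it through.** **The plan's own figure.** Power Analyses states more than 90% power. On clinic means, with SD 2.5 points and 12 clinics per arm, SE = 2.5 × √(2/12) = 1.02. For 2% v 7%, 5/1.02 = 4.90 and Φ(4.90 − 1.96) = 99.8%; with a t reference, power is 99.7% (22 df) or 99.6% (20 df). For 1% v 7%, as the result sentence is worded, power exceeds 99.9%. The stated figure is met.

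**Exact simplest case.** Take 24 equally weighted clinics with normal clinic-level outcomes, and covariates balanced between arms. The uncorrected sandwich variance of the arm difference is RSS/144. The unbiased one is (RSS/df) × (1/6). Their ratio is df/24, so the true size of the z-test is P(|t_df| > 1.96 × √(df/24)).

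| Clinic-level model | df | Effective cut-off | Size | Interval narrower than exact t |
|---|---|---|---|---|
| Arm only | 22 | 1.877 | 7.4% | 9.5% |
| + baseline rate | 21 | 1.833 | 8.1% | 11.8% |
| + health system | 20 | 1.789 | 8.9% | 14.2% |

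These figures need only the number of clinics and of clinic-level parameters.

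**Simulation of the AR(1) logistic GEE under the null.** Two separately coded simulations used clinic-month counts, post-intervention months as outcome and baseline rate as covariate. The first used 90 smokers per clinic-month (the power paragraph's figure) and 5,000 trials per setting. The second used mostly 120 (the analysis paragraph's figure) and 4,000. Both covered 6 months, since "rates of referral to the WTQL from all 24 clinics will be monitored for 6 months after the initial training", and 12 months, since Table 1 gives a 12-month implementation phase. Assumed, because the documents do not give them: the distribution of clinic rates, baseline-to-post correlation 0.5, month-to-month variation, spread of clinic size (CV 0 to 0.5), and the system effect. SD 2.5% was read as between-clinic SD. The first simulation also used 1.2%, which is what remains if 2.5% is the SD of one clinic-month rate: √(2.5² − 2.19²), where 2.19 = 100 × √(0.045 × 0.955/90).

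Arm effect, uncorrected sandwich with z:

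- System omitted, no system effect: 8.3–11.5% (first), 9.3–13.1% (second).
- System omitted, system matters: 5.1–10.8% when it explains 20–30% of between-clinic variance (first); 10.6% and 9.7% for system effects of ±30% and ±60% (second).
- System in the model: 8.9–13.4% (first); 11.6% and 14.1% for the same two effects (second).

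A third, simpler simulation gave about 10% without and 12% with system when it has no effect, and about 7.5% and 12% when it explains 25% of the variance.

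Model-based AR(1) errors with z did worse, at about 9–20% over 6 months.

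With system in the model and t on 20 df, Mancl-DeRouen gave 3.3–4.5% (first) and 3.7% and 4.5% (second). Kauermann-Carroll gave 5.0–7.5% (first), and a Kauermann-Carroll-type version gave 6.4% and 7.8% (second).

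**Other tests (first simulation).** For quality referral, rates were referral rates × 41%, the fax enrolment share in the Background. The uncorrected test ran at 7.5–11.6% without and 9.2–13.0% with system, and Mancl-DeRouen with t at 3.3–4.3% with system. For condition by occasion, the uncorrected test ran at 7.3–10.1% and Mancl-DeRouen with t at 4.0–5.6%.

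**The case against.** The best reply is that the inflated rate belongs to a test the plan never names. A generalized score test is equally compatible with the text; with system omitted but influential, it ran at 2.3–5.9% in the first simulation. That stands. The documents leave the test open and do not show a miscalibrated one, so a reader who infers that the primary analysis will run at 8–13% goes beyond them.

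A reader might also infer that leaving out the stratum causes the inflation. The results show the opposite: when system matters, omitting it lowers rejection. The sponsor gives a reason for one covariate, and that covariate is itself one of the urn-balanced factors. The cost of relaxing the rule is small, however: the t critical value moves from 2.080 (21 df) to 2.086 (20 df).

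It is also fair to say that the planned effect is large, and that the simulated ranges rest on assumptions and are not bounds; the two simulations do not coincide. Nor did they test the reading in which baseline and post-intervention phases are both outcomes with a condition-by-period interaction. These points limit the size of the claim. They do not supply the missing specification, and the exact simple case does not depend on the assumed clinic variation.

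**Conclusion.** The omission is certain: the plan does not fix how a 24-cluster GEE will be tested, and no other section does. The consequence is conditional. If the uncorrected sandwich Wald z-test is used, size is 7.4–8.9% in the exact simple case and about 8–13% under the assumed clinic variation with no system effect, with intervals too narrow. The missing stratum is a separate matter of precision and conservatism. It is linked to the first only because adding system without a correction makes the z-test more liberal.

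The documents do not support the stronger reading that the main referral finding is at risk. At 2% v 7% that conclusion is unlikely to change. Quality-referral power was 87% or more when 41% enrolment was assumed in both arms; lower enrolment after eReferral was not computed. The benefit lies in interval coverage, the quality-referral outcome and the condition-by-occasion test. The plan should be changed, but this is not a fatal flaw.

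**What to change.** In the primary-analysis paragraph:

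1. Add health system to the model alongside the baseline rate.
2. Test the arm effect with one bias-corrected sandwich named in advance, for example Mancl-DeRouen or Kauermann-Carroll, and t on clinics minus clinic-level parameters: 24 − 4 = 20 df (intercept, arm, baseline rate, system).
3. Take intervals from the same covariance and t distribution.
4. Apply the same rule to quality referral and to condition by occasion.

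Make the changes together, for the reason given above.

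The cost is about two sentences, one model term and 1 df. With system in the model, intervals were 29–40% (Mancl-DeRouen) or 17–21% (Kauermann-Carroll) wider than uncorrected ones. In the first simulation's least favourable setting (SD 2.5% in both arms), power for 2% v 7% was 88–93% with Mancl-DeRouen and 92–95% with Kauermann-Carroll. That is not a floor: in the second simulation, with system omitted, Mancl-DeRouen power fell to about 81% when clinic SD equalled the arm mean, wider than planned. Kauermann-Carroll loses less power but is slightly liberal. Whether PROC GENMOD offers the chosen correction directly was not checked and should be confirmed before it is named.
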